9.3.4. Tertiary/Exploratory Analysis

Exploratory endpoints are listed in Section 3.

The average of AUC (Day 120-180) and AUC (Day 210-270) of the ApoB reduction will be calculated for participants with complete ApoB measurements during the specified period.

The calculated AUCs will be analyzed using an ANCOVA model. Baseline ApoB measurements will be used for adjustment. A Bayesian approach will be used as the dose-response model for time averaged AUC measures. The placebo group will be modeled with LY3561774 doses.

Details of the prior distribution specifications along with other analyses used for the exploratory objectives will be provided in the SAP.

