1.2. Study Design

Study EZCB is a Phase 2, randomized, double-blind, placebo-controlled, parallel-arm study to investigate the efficacy and safety of LY3561774 in adults with mixed dyslipidemia.

Participants will be randomly assigned in a 2:1:2:2 ratio to placebo: LY3561774 100 mg:400 mg:800 mg. Placebo participants will be randomly assigned such that each dose cohort will have a matching placebo cohort that receives the same dose volume to maintain the study blind.

Participants will be stratified according to the Visit 1 TG level of less than 250 mg/dL and 250 mg/dL or greater.

Study intervention administration is by subcutaneous injection. Dosing will occur twice during the study, on Day 0 and Day 90 ± 5 days.

If a participant's ApoB levels do not return to 80% of baseline or higher on Day 270, then the participant will continue to the follow-up visit at Day 360.

If a participant's ApoB levels return to ≥80% of baseline or higher on Day 270, then Day 270 is the participant's last study visit.

Figure EZCB.1.1 illustrates the study schema.

2. Statistical Hypotheses

The Study EZCB hypothesis for the primary objective is that at least one dose of LY3561774 100 mg, 400 mg, or 800 mg is superior in percent change from baseline for ApoB relative to placebo at Day 180 in participants with mixed dyslipidemia.

Thus, the null hypothesis to be tested in relation to the primary estimand is that LY3561774 100 mg, 400 mg and 800 mg are not different from placebo with respect to percent change in ApoB from baseline to Day 180.

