4.5.4. Bayesian Analyses for Dose-Response

A Bayesian dose-response analysis will be performed on the percent change from baseline at Day 180 and the percent change from baseline for time-averaged parameters from Day 30 to Day180 and from Day 120 to Day 270 for the parameters

- ApoB, and
- non-HDL-C.

The longitudinal model, a proportional discrete time model (PDT), will be used to estimate Bayesian dose response. The PDT model assumes that the efficacy of the modelled treatment plateaus after some time point, Q. Let $y_{it}(d)$ represent the change from baseline ApoB at time t for participant i receiving dose d. Then the PDT can be written as

$$y_{it}(d) = \mu(t_l, d, \theta) + g(t) * s_i + \epsilon_{it}$$

with the mean function

$$\mu(t_l, d, \theta) = \lambda(d) \{ p_l * I(t_l < t_0) + I(t_l \ge t_0) \}$$

where $s_i \sim N(0, \sigma_s^2)$ and $\epsilon_{it} \sim N(0, \sigma^2)$, $\theta = (\lambda(d), p_1, ..., p_{Q-1})'$, and p_l represents the proportion of the efficacy of dose level d, $\lambda(d)$, at time t_l , for $t_l < t_Q$. Based on the data from the above, we may assume $t_Q = \text{Day } 30$. The function, g(t), may be specified to allow the errors to be proportional to the time trend of the mean response. An example of such a function that also incorporates a plateau in efficacy (Qu et al. 2019) is

$$g(t) = \{p_l * I(t_l < t_Q) + I(t_l \ge t_Q)\}.$$

A simple normal dynamic linear model may be assumed for the dose-response function, $\lambda(d)$:

$$\lambda(1) \sim N(0, \sigma_{\lambda}^{2})$$
$$\lambda(d) \sim N(\lambda(d-1), \sigma_{\lambda}^{2}) \text{ for } d > 1$$

The estimation of the parameters will be carried out in a Bayesian framework, assuming non-informative priors for the hyperparameters:

$$p_l \sim U(0,1)$$

$$1/\sigma^2, 1/\sigma_s^2, 1/\sigma_\lambda^2 \sim Gamma(0.01, 0.01)$$

Posterior inference will be drawn for the dose response at time t of clinical interest and the 95% credible intervals will also be plotted.

Alternative dose-response models, including the three-parameter logistic regression or power model, may also be considered for $\lambda(d)$, if the dose-response model does not fit the data well. Some alternative dose-response models are

• Three-parameter logistic model

$$\lambda(d) = \alpha_0 + \frac{\alpha_1 d^*}{\alpha_2 + d^*}$$

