where parameters α_0 , α_1 , and α_2 represent the basal effect when the dose level is zero (placebo), the maximum effect that can be achieved by any dose level on top of placebo, and the dose level that produces half of the maximum improvement (ED₅₀), respectively. Here, d*, represents the actual dose (for example, in mg) versus dose level (1, 2, 3, and so on).

Power model

$$\lambda(\mathbf{d}) = \alpha_0 * \alpha_1 \mathbf{d}^{*\gamma}$$

where α_0 and α_1 represent the basal effect for the placebo group and the slope, respectively, and γ is a sigmoidicity parameter indicating shape or steepness of the dose response. Here, d^* , represents the actual dose (for example, in mg) versus dose level (1, 2, 3, and so on).

Furthermore, if the PDT model, or any related longitudinal model, does not fit the data well, these or other dose-response models may be fitted to the percent change from change from baseline at Day 180, and the percent change from baseline for time-averaged parameters from Day 30 to Day 180 and from Day 120 to Day 270 for the parameters, excluding the intermediate timepoints.

The same dose-response models may be fitted to the percent absolute change from baseline for magnetic resonance imaging (MRI) hepatic fat fraction at Day 180 and the time-averaged endpoints. These models will not require additional longitudinal modeling, and will take place after imputation for missing data according to the efficacy estimand for the time-averaged analysis and the treatment policy estimand for the hepatic fat fraction analysis.

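### The optional power dose-response model in SAP 4.5.4 is printed as a product, which fixes the placebo response at zero and contradicts its own parameter definitions (minor)

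*SAP*

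**What the plan says.** SAP 4.5.4 plans an exploratory Bayesian dose-response analysis of ApoB and non-HDL-C. The default for `λ(d)` is a normal dynamic linear model. If that fits poorly, "Alternative dose-response models, including the three-parameter logistic regression or power model, may also be considered".

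Two alternatives are written out:

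- Three-parameter logistic: `λ(d) = α0 + α1 d*/(α2 + d*)`, with `α0` described as the effect at dose zero.
- Power: `λ(d) = α0 * α1 d*^γ`. Here `α0` and `α1` "represent the basal effect for the placebo group and the slope, respectively". The exponent `γ` governs how steep the curve is.

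For both, `d*` is the dose actually given (in mg, for example) rather than a rank, so placebo is `d* = 0`. The section gives priors for the visit proportions and the three precisions, but none for `α0`, `α1` or `γ`. It also allows the same models for the time-averaged endpoints and for MRI hepatic fat fraction. Protocol 9.3.4 says of this analysis: "The placebo group will be modeled with LY3561774 doses".

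**The concern.** A parameter described as the placebo effect should be the model's value at dose zero. In the logistic model it is. In the power model as printed, `α0` multiplies a term that vanishes at dose zero, so it cannot play that part. It also appears only in combination with `α1`, so the data cannot tell the two apart.

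At stake is a prespecified formula that cannot deliver the quantities the SAP attaches to it. Placebo participants would be in the fit, as the protocol requires, but their mean would be fixed rather than estimated. Anyone who then read a placebo-adjusted effect off the fitted curve would be subtracting zero in place of the placebo response.

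**Working it through.** No figure in either document depends on this formula, so there is no stated result to reproduce. The check is algebra, followed by an illustration.

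**Inputs.** The power and logistic equations and parameter definitions come from SAP 4.5.4. The doses 0, 100, 400 and 800 mg and the 2:1:2:2 allocation come from SAP 1.2. Completers come from Protocol 9.5: 175 × 2/7 = 50 and 175 × 1/7 = 25 randomised, and with 20% dropout 40 and 20, so 40/20/40/40.

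**Step 1: value at placebo.** With `γ > 0`, `0^γ = 0`, so `λ(0) = α0·α1·0 = 0` for every `α0` and `α1`. The SAP gives no range for `γ`. `γ = 0` makes the curve flat and `γ < 0` leaves it undefined at placebo, so neither rescues the definition. No other term supplies an intercept: in the longitudinal model the mean is `λ(d)` times a visit factor, and the participant effect and the residual both have mean zero.

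**Step 2: identifiability.** Take `γ = 0.5`, so that `d*^γ` is 0, 10, 20 and 28.28. The pairs (`α0`, `α1`) = (−2, 0.5), (−1, 1), (−4, 0.25) and (10, −0.1) all have product −1, and all give 0, −10, −20 and −28.28. The matrix of derivatives with respect to (`α0`, `α1`, `γ`) over the four doses has rank 2 of 3. For the additive form `α0 + α1 (d*)^γ` the rank is 3 of 3 and `λ(0) = α0`.

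**Step 3: consequence if used as printed.** The effects and placebo changes here are assumptions; the documents give none for this purpose. Take true differences from placebo of −12, −24 and −30 points, add a placebo change, and fit each form by least squares weighted 40/20/40/40.

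| Placebo change | True active means | Product-form active means | Error in active means |
|---|---|---|---|
| −5 | −17, −29, −35 | −17.9, −28.2, −35.4 | −0.9, +0.8, −0.4 |
| +5 | −7, −19, −25 | −8.6, −17.8, −25.6 | −1.6, +1.2, −0.6 |

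The active-dose means are off by at most 1.6 points. The additive fit is off by at most 1.1 in the same scenarios, because no power curve passes exactly through these means.

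The product form's fitted placebo value is 0, so its model-based differences from placebo equal the active means in the table. The additive form gives −13.2, −23.1 and −30.6 in both scenarios. Product minus additive is then:

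- placebo −5: −17.9 + 13.2 = −4.7; −28.2 + 23.1 = −5.1; −35.4 + 30.6 = −4.8
- placebo +5: −8.6 + 13.2 = +4.6; −17.8 + 23.1 = +5.3; −25.6 + 30.6 = +5.0

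The shift is therefore about the size of the placebo change and similar at all three doses.

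**Step 4: a second assumed curve.** With true differences of −10, −20 and −30, the product-form difference at 800 mg is −34.7, −31.8, −29.8, −27.9 and −25.1 for placebo changes of −5, −2, 0, +2 and +5. The additive form gives −29.8 each time. With no placebo change the two forms agree.

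**The case against.** The strongest objection is that everything rests on one symbol in text read from a PDF. That section shows at least one other doubtful symbol: the plateau time appears as `t_0` in the mean function but as `t_Q` in the surrounding text. Every word around the power model fits a plus sign, as does the additive model above it. This stands as a reason to look at the source page before changing anything; if it prints a plus, the point closes. It does not dispose of the point now, because the same section shows a plus sign in the logistic model and uses the asterisk for products elsewhere. Reading the formula as `α0 (α1 d*)^γ` leaves both defects in place. Only `α0·α1^(d*^γ)` would return `α0` at placebo, and that is neither what is printed nor consistent with calling `α1` a slope.

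Second, the model is one optional example in an exploratory analysis, and the SAP also leaves room for other models. A competent programmer would probably see the intent from the definitions, and a non-identified pair would usually show in sampling diagnostics. This stands and limits the severity.

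Third, section 4.5.4 promises posterior inference on the dose response and does not prescribe a contrast of `λ(d)` with `λ(0)`. This also stands: the error appears only if such a contrast is taken from the fitted model.

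**Conclusion.** As printed, the power model contradicts its own definitions: placebo is fixed at zero and `α0` and `α1` cannot be separated. This follows from the equation for any `γ > 0` and needs no assumed data. The practical effect is conditional. If the model is used and differences from placebo are read from it, they are off by roughly the true placebo change, about 5 points for an assumed 5 and none for zero.

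Three stronger readings are tempting but not supported:

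- A reader might infer that placebo drift is absorbed into the active-dose curve. In the illustration the fitted active means stay within 1.6 points of the truth, and the large error sits at the placebo point.
- A reader might infer a large percentage bias concentrated at 100 mg. The shift is nearly equal across doses. A percentage at 100 mg would depend on the assumed effects and would partly reflect power-curve misfit that the additive form shares (−13.2 against an assumed −12).
- A reader might infer that the SAP commits to this model when the default fails, or that the main results are exposed. The wording is permissive, and the primary MMRM, the sample size, the power and the alpha do not involve it.

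Minor severity, subject to confirming the operator on the source page.

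**What to change.** Check the operator in the power model on the source page of SAP 4.5.4. If it is a product, replace the formula with `λ(d) = α0 + α1 (d*)^γ`, `γ > 0`. `α0` is then the placebo response and `α1` the slope, as the text already says, and the form matches the additive three-parameter model above it. Add that placebo-adjusted effects are taken as `λ(d) − λ(0)`, and state priors for `α0`, `α1` and `γ`, which the section does not give.

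The cost is one symbol and a line or two of text. No data, design, sample-size or primary-analysis change follows.

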4.5.5. Immunogenicity Assessments

If data from validated immunogenicity assays are available, treatment-emergent-ADAs may be assessed.

Treatment-emergent ADAs are defined as participants

- with a 2-fold (1 dilution) increase in titer than the minimum required dilution if no ADAs were detected at baseline (treatment-induced ADA), or
- with a 4-fold (2 dilutions) increase in titer compared with baseline if ADAs were detected at baseline (treatment-boosted ADA).

The frequency and percentage of participants with preexisting ADA and who are treatment-emergent-ADA positive (TE-ADA+) to LY3561774 will be tabulated.

The distribution of titers and frequency of neutralizing antibodies (if assessed) for the treatment-emergent-ADA+ participants may also be tabulated.

The relationship between the presence of antibodies and PK parameters, efficacy response, or safety to LY3561774 may also be assessed.

4.6. (Other) Safety Analyses

Unless otherwise specified, safety will be assessed by comparing safety of LY3561774 doses with placebo irrespective of adherence to study drug. Thus, safety analyses will be conducted using the SAS.

4.6.1. Extent of Exposure

Duration of exposure will be calculated as number of days participant was on-treatment, as defined in Section 4.1. Summary of duration of exposure will be provided by treatment group using data from the SAS. The descriptive statistics n, mean, SD, median, minimum, maximum, and sum (that is, total participant-years of follow-up) will be provided. In addition, the number of participants who received 1 or 2 doses will be summarized by counts and percentages.

4.6.2. Adverse Events

A TEAE is defined as an event that first occurred or worsened in severity after first dose. The Medical Dictionary for Regulatory Activities (MedDRA) Lowest Level Term (LLT) will be used in the treatment-emergent derivation. The maximum severity for each LLT during the baseline period, including ongoing medical history, will be used as baseline severity. Events with a missing baseline severity will be treated as "mild" in severity for determining treatment-emergence. Events with a missing severity during the postbaseline period will be treated as "severe" and treatment-emergence will be determined by comparing to baseline severity.

For events occurring on the day of first taking study medication, the case report form collected information (for example, treatment emergent flag, start time of study treatment, and event) will be used to determine whether the event was pre- versus post-treatment if available. If the relevant information is not available, then the events will be counted as posttreatment.

The counts and percentages of participants with TEAEs will be summarized by treatment using MedDRA Preferred Term (PT) nested within the System Organ Class (SOC). Statistical comparisons will be applied at both the SOC and PT levels. Events will be ordered by decreasing frequency within SOC. The SOC will be in alphabetical order. For events that are sex-specific, the denominator and computation of the percentage will include only participants from the given sex

An overview of the number and percentage of participants who experienced a TEAE, serious adverse event (AE), death, discontinued from study treatment or study due to an AE, and TEAE relationship to study drug will be summarized by treatment.

The counts and percentages of patients with TEAEs by maximum severity will be summarized by treatment using MedDRA PT. For each participant and TEAE, the maximum severity for the MedDRA PT is the maximum postbaseline severity observed from all associated LLTs mapping to the MedDRA PT. The maximum severity will be determined based on the non-missing severities. If all severities are missing for the defined postbaseline period of interest, it will show as missing in the table.

4.6.3. Patient Narratives

Patient narratives contain patient level data and a summary paragraph. Patient narratives will be provided for participants in the randomized population with at least one notable event. Notable events include death, serious adverse events, and permanent discontinuation of study treatment due to an adverse event.

4.6.4. Vital Signs

If multiple records of a participant's vital signs are collected at the same visit, they will be averaged prior to being used for data summaries and analyses.

Descriptive summaries by treatment and by nominal visit will be provided for baseline and postbaseline values as well as change from baseline values.

Treatment differences in mean change will be analyzed using the MMRM model as described in Section 4.3.2

Counts and percentages of participants with treatment-emergent abnormal sitting systolic blood pressure (BP), sitting diastolic BP, and pulse rate will be presented by treatment group. Both planned and unplanned measurements will be included in the analysis. Counts and percentages of participants with treatment-emergent abnormal sitting systolic blood pressure (BP), sitting diastolic BP, and pulse will be presented by treatment for participants who have both baseline and at least 1 postbaseline result. A treatment-emergent high result is defined as a change from a value less than or equal to the high limit at baseline, to a value greater than the high limit at any time, that meets the specified change criteria during the postbaseline period. A treatmentemergent low result is defined as a change from a value greater than or equal to the low limit at baseline, to a value less than the low limit at any time, that meets the specified change criteria during the postbaseline period. To assess decreases, change from the minimum value during the baseline period to the minimum value during the postbaseline period will be used. To assess increases, changes from the maximum value during the baseline period to the maximum value during the postbaseline period will be used. Both planned and unplanned measurements will be included in the analysis. The criteria for identifying patients with treatment-emergent vital sign abnormalities are stated in Table EZCB.4.3.

Table EZCB.4.3 Categorical Criteria for Abnormal Treatment-Emergent Blood Pressure and Pulse Measurements

Parameter	Low	High
Systolic BP (mm Hg)	≤90 and decrease from	≥129 and increase from
(supine or sitting)	baseline ≥20	baseline ≥20
Diastolic BP (mm Hg)	≤50 and decrease from	≥90 and increase from
(supine or sitting)	baseline ≥10	baseline ≥10
Pulse (bpm)	<50 and decrease from	>100 and increase from
(supine or sitting)	baseline ≥15	baseline ≥15
Weight (kg)	(Loss) Decrease ≥7%	(Gain) Increase ≥7%

Abbreviations: BP = blood pressure; bpm = beats per minute.

Counts and percentages of participants with maximum systolic blood pressure and diastolic blood pressure will be summarized by treatment groups for the categories listed in Table EZCB 4.4, using the SAS.

Table EZCB 4.4 Categorical Criteria for Summaries of Maximum Blood Pressure

Systolic BP (mm Hg)	Diastolic BP (mm Hg)
<90	<60
≥90	>60
≥120	>90
≥140	>110
≥160	≥120
≥180	-

Abbreviation: BP = blood pressure.

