- 26. Have active severe liver diseases, such as cirrhosis, active hepatitis, or biliary obstruction with hyperbilirubinemia.
- 27. Have a history of infection within 14 days before screening that, in the opinion of the investigator, would potentially affect participant safety within the study or interfere with the interpretation of data.
- 28. Have HIV infection or are positive for HIV antibodies.
- 29. Have current infection with hepatitis B virus or positive for hepatitis B surface antigen.
- 30. Have a current infection with hepatitis C virus or positive hepatitis C virus antibody.

Diagnostic assessments

- 31. Have clinically relevant anemia, as defined by the investigator.
- 32. Have laboratory values, in relation to the reference range,
 - ALT >3.0X ULN or
 - ALP >1.5X ULN or
 - TBL >1.5X ULN, except for participants diagnosed with Gilbert's syndrome.
- 33. Have an eGFR <30 mL/min/1.73 m².
- 34. Have a pulse rate >100 bpm, a repeat measure is allowed.
- 35. Have uncontrolled hypertension with a resting blood pressure ≥180 mm Hg systolic and/or ≥100 mm Hg diastolic, a repeat measure is allowed.

Prior/concomitant therapy

- 36. Have used or are taking products for the purpose of lowering lipid levels. This includes lipid-regulating medication, over-the-counter products, or herbal therapies.
See Section 10.7.3 for details on prohibited treatments and the timeframe relative to screening.
Exceptions: Statins, PCSK9 inhibitors, bempedoic acid, and ezetimibe.
- 37. Have within 3 months of screening, initiated treatment with SERMs, estrogens, progestins, testosterone, or thyroid hormone therapy.
- 38. Have or are currently taking HIV protease inhibitors, cyclophosphamide, or systemic retinoids.
- 39. Have within 6 months of screening had treatment with any oligonucleotide, including small interfering ribonucleic acid.
Exception: mRNA vaccines.
- 40. Have within 3 months of screening treatment with systemic corticosteroids, cyclosporine, isotretinoin, or anabolic agents.
Exceptions: local, topical, intra-articular, inhalation, or nasal corticosteroids.
- 41. Have within 1 month prior to screening treatment with
 - a. warfarin or other coumarins
 - b. direct thrombin inhibitors
 - c. Factor Xa inhibitors, or

- d. Heparins or heparinoids.
42. Are currently using a medication associated with weight gain or weight loss.

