(Treatmen t k vs. Reference Arm)	SE	$e^{\bar{Z}_{b}} \sqrt{e^{2\hat{\mu}_{\Delta Z,k}} \cdot \left(\widehat{SE}_{\Delta Z,k}\right)^2 + e^{2\hat{\mu}_{\Delta Z,R}} \cdot \left(\widehat{SE}_{\Delta Z,R}\right)}$	$\exp(\hat{\mu}_{\Delta Z, k \ vs \ R}) \cdot \widehat{SE}_{\Delta Z, k \ vs \ R} \times 100$
12)	P-value	NR	P∆Z,k vs R
	95% CI	Estimate $\pm \Phi^{-1} (1 - \frac{\alpha}{2}) * SE$	$(\left[\exp\left(L_{\Delta Z,k\ vs\ R}\right)-1\right]\times 100, \left[\exp\left(U_{\Delta Z,k\ vs\ R}\right)-1\right]\times 100)$

Abbreviation: CI = confidence interval; NR = not reported; SE = standard error.

In general, a time-averaged parameter will refer to the area under the curve (AUC) constructed using the trapezoidal rule, applied to the parameter according to the scheduled time, divided by the length of observation. For example, a time-averaged dependent variable for Days 30 to 180 will equal AUC/150, where AUC represents the AUC constructed by the trapezoidal rule.

Unless otherwise specified, baseline is defined as the last non-missing measurement recorded on or before the randomization visit, prior to first dose of intervention.

When considering treatment-emergent abnormal safety laboratory values and vital signs, baseline observation will start from the screening visit and end prior to, or at, the randomization visit, wherein all scheduled and unscheduled measurements will be included. The baseline for the treatment-emergent safety analysis will be the maximum/minimum from all measurements taken during the baseline period. For postbaseline measurements, all scheduled and unscheduled measurements in the analysis period will be included. The maximum/minimum from all measurements taken during the analysis period will be used in the treatment-emergent safety analysis. The end of Study EZCB participation for a participant will be the earliest of date of death, the date of withdrawal from further participation in the study, or the date of the safety follow-up visit (Visit 801). For participants considered to be lost to follow-up, end of Study EZCB participation will be the date participant is lost to follow-up as reported by the investigator. Participant data included in the database after the last date of Study EZCB participation (including the safety follow-up period) will be excluded from statistical analysis.

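### SAP 4.6.4 and Table EZCB.4.3 disagree on when a blood pressure counts as treatment-emergent high or low, and the stated denominator includes participants who cannot have the event

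*SAP*

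**What the plan says.** SAP 4.6.4 (Vital Signs) defines the event in its text. The starting point for a high result is given as follows: "A treatment-emergent high result is defined as a change from a value less than or equal to the high limit at baseline". The text then requires the later reading to move strictly past that limit, that is, "to a value greater than the high limit at any time, that meets the specified change criteria during the postbaseline period". The low result mirrors this: baseline at or above the low limit, followed by a move "to a value less than the low limit at any time, that meets the specified change criteria during the postbaseline period".

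The same section sends the reader to Table EZCB.4.3 for the criteria. The systolic high entry there is "≥129 and increase from" baseline of at least 20, and the diastolic high entry is "≥90 and increase from" baseline of at least 10. The low entries are systolic 90 or less with a fall of at least 20, and diastolic 50 or less with a fall of at least 10. All four are inclusive, and none has a baseline condition. The pulse row uses strict signs and agrees with the text.

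Three other provisions matter:
- Denominator (SAP 4.6.4): counts and percentages are given "for participants who have both baseline and at least 1 postbaseline result".
- Baseline (SAP 4.1): "The baseline for the treatment-emergent safety analysis will be the maximum/minimum from all measurements taken during the baseline period".
- Eligibility (Protocol 5.2, criterion 35): exclusion starts at "resting blood pressure ≥180 mm Hg systolic and/or ≥100 mm Hg diastolic", so systolic 130 to 179 and diastolic 91 to 99 can be enrolled.

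Protocol 9.3.5.1 compares these percentages between treatment groups by Fisher's exact test.

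**The concern.** No sentence says how text and table fit together, so two programmers could produce different counts from the same data. They could differ on readings exactly at a limit, and on whether someone already above the limit can have an event.

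The denominator matters more. If the baseline condition applies, a participant who enters with a systolic maximum above 129 cannot be an event however far the pressure rises, yet still counts in the percentage. Taking the maximum of all baseline-period readings enlarges that group. The reported percentage is then neither a risk among those who could have the event nor a count of all large rises. Comparing the safety of the study drug with placebo is a stated secondary objective, and the arms are small (175 × 2/7 = 50, or 175/7 = 25 for the 100 mg arm).

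**Working it through.** **1. Text and table side by side.** Write b for the baseline value, p for the post-baseline extreme, L for the limit and c for the required change. For a high result:
- text: b ≤ L, p > L and p − b ≥ c
- table alone: p ≥ L and p − b ≥ c

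| Parameter | b to p | Table alone | Text | Reason for difference |
|---|---|---|---|---|
| Systolic high | 109 to 129 | event | no | sign |
| Systolic high | 110 to 130 | event | event | none |
| Systolic high | 130 to 150 | event | no | baseline condition |
| Systolic high | 150 to 185 | event | no | baseline condition |
| Diastolic high | 80 to 90 | event | no | sign |
| Diastolic high | 91 to 101 | event | no | baseline condition |
| Systolic low | 110 to 90 | event | no | sign |
| Diastolic low | 60 to 50 | event | no | sign |

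Every text event is also a table event, so the text can only lower the count. This step needs no assumptions.

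**2. Dilution.** If a share q of participants has b > L, then

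reported incidence = incidence among those at risk × (1 − q).

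The absolute difference between arms shrinks by the same factor. The ratio between arms does not change.

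**3. Size.** The documents give no figure to reproduce for this rule and no baseline blood pressure, so the inputs are assumptions. I simulated systolic readings with SD 14 and within-person correlation 0.6 (between-person variance 0.6 × 196 = 117.6, within-person 0.4 × 196 = 78.4), rounded to 1 mm Hg, with screening systolic below 180. The Schedule of Activities gives two baseline visits (1 and 2) and ten post-baseline visits (3 to 12).

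Share not at risk (maximum baseline above 129):

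| Mean systolic | 120 | 125 | 130 | 135 |
|---|---|---|---|---|
| q | 36% | 51% | 66% | 79% |

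At mean 130, a 5 mm Hg rise on active treatment against none on placebo:

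| Rule | Active | Placebo | Difference | Ratio |
|---|---|---|---|---|
| Text, stated denominator | 13.6% | 6.5% | 7.1 points | 2.1 |
| Text, at-risk denominator | 40.1% | 19.2% | 20.9 points | 2.1 |
| Table alone, no baseline condition | 25.0% | 10.7% | 14.3 points | 2.3 |

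Check against step 2: 40.1% × 0.34 = 13.6% and 19.2% × 0.34 = 6.5%.

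A second set of assumptions (mean 120 to 140, between-person SD 13, within-person SD 7 to 9) leaves 35% to 85% not at risk. A 10 mm Hg rise then adds 7 to 23 points with the stated denominator, 30 to 46 among those at risk, and 28 to 35 with no baseline condition.

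**4. The inequality signs alone.** For systolic high, making the post-baseline limit inclusive moves incidence by 0.1 to 0.6 points. For diastolic (mean 80, SD 9, same correlation, **no** treatment effect), text against table is 12.0% v 14.7%. If 20% of readings are rounded to the nearest 10, it is 12.2% v 18.4%, a gap of 6.2 points, of which the sign accounts for about 5.

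**The case against.** The strongest reply is that text and table form one rule. The text leaves its limits and change criteria to the table, and the table leaves the meaning of treatment-emergent to the text. On that reading, 150 to 185 is plainly not an event, and the stand-alone table rule appears only if the text is ignored. This is the likelier intention, and I accept it. It does not remove the sign conflict at the four blood-pressure limits, and it is the reading under which the denominator is wrong.

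A reader might also infer that the blood-pressure safety result as a whole depends on which sentence is followed, or that a rise could go unseen. The documents do not support that. SAP 4.6.4 also plans by-visit summaries, an MMRM of mean change, and maximum blood-pressure categories up to 180 or more (Table EZCB 4.4) with no baseline condition. The participant going from 150 to 185 appears there. Nor is there bias between arms: randomization makes the not-at-risk share equal in expectation, and the ratio stays near 2 under every rule.

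The at-risk denominator also recovers little power. In the mean-130 scenario, Fisher power is about 12% with 50 v 50 under the stated denominator, 16% with about 17 v 17 at risk (50 × 0.34), and 37% with no baseline condition. The gain is mainly an interpretable percentage. Finally, blood pressure is not among the potential risks named in Protocol 2.3.1.

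**Conclusion.** The point holds as an internal inconsistency and a mismatched denominator in one categorical safety analysis. The sign conflict is certain, trivial in size for systolic pressure, and possibly about 5 points for diastolic pressure if readings are rounded to the nearest 10. With the baseline condition applied, incidences and absolute differences are diluted by the share not at risk, and large rises in participants already above the limit go uncounted in this analysis. The problem lies mainly on the high side, since few participants are likely to enter below 90 systolic or 50 diastolic.

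The size (36% to 79% not at risk; a 7.1-point difference where those at risk show 20.9) rests on assumed baseline pressures and should be read as a range. Severity: minor.

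**What to change.** Amend SAP 4.6.4 and Table EZCB.4.3 before unblinding:
- Reconcile text and table into one rule, with the same inequality signs in both, so that a reading exactly at a limit is classified one way at baseline and after dosing.
- State the baseline condition explicitly, in or beside the table.
- Compute the percentages and Fisher's exact test among participants who meet that condition, separately for high and low.
- On a separate line by arm, report how many participants already beyond the limit at baseline meet the change criterion.

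The cost is SAP wording and programming; no visit, procedure or data collection changes. The downside is smaller denominators that differ by parameter and must be shown in the table.
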